3.6 Study stopping guidance

The following stopping rules will apply at relevant key instances in the ALIVE study:

- **ISGIODAI** Barcelona Institute for Global Health
 - The occurrence of ≥1 serious adverse reaction (where causality is at least possible) or SUSAR in any of the weight groups in the Phase II will result in suspension of dose escalation in the FDC arm pending review by the DSMB (keeping in mind the sequential recruitment strategy in phase II).
 - 2. The occurrence of ≥2 serious adverse reactions or SUSARs at the end of phase II will result in suspension of progress to phase III pending review by the DSMB.

Overall the occurrence of serious adverse reactions or suspected unexpected serious adverse reactions in 2% of the study populations at interim analysis (50% recruitment) will result in suspension of further dosing of the Investigational Product pending review by the DSMB. This is equivalent to 12 safety events which meet these criteria in 612 participants recruited at the point of the interim analysis.

Table 3. Sample size and power calculation according to the expected efficacy (Cure Rate) of the different treatment arms

Comparison Trichuris trichiura	Target Power	Actual Power	Sample Size	Expected Cure Rate	Overall Alpha	Bonferroni adjusted Alpha
ALB vs IVM-ALB vs (IVM-ALB)x3 IVM-ALB vs (IVM-ALB)x3	80% 80% 80%	91% 100% 80%	116 223 223	23.7% 43.7% 59%	0.05 0.05 0.05	0.0167 0.0167 0.0167
Strongyloides stercoralis ALB vs IVM-ALB vs (IVM-ALB)x3	80% 80%	95% 100%	42 108 107	45% 79% 94%	0.05 0.05	0.0167 0.0167
IVM-ALB vs (IVM-ALB)x3 Hookworm ALB vs IVM-ALB vs (IVM-ALB)x3 IVM-ALB vs (IVM-ALB)x3	80% 80% 80% 80%	80% 82% 80%	91 91 99	79.5% 79.5% 95%	0.05 0.05 0.05 0.05	0.0167 0.0167 0.0167 0.0167

	Pł	nase II		PHASE III		PHASE II/III
		N total			N tota	al
		Phase			Phase	
Group	N	II ¹	Ν		III ¹	N total
Trichuris trichiura						
ALB	23	26	93		103	129
FDCx1	45	50	178		198	248
FDCx3	45	50	178		198	248
Total	113	126	449		499	625
Strongyloides.						
stercoralis						
ALB			42		47	47
FDCx1			108		120	120
FDCx3			107		119	119
Total		0	257		286	286
Hookworm						
ALB			91		101	101
FDCx1			91		101	101
FDCx3			99		110	110
Total		0	281		312	312
TOTAL		126			1097	1223

Table 4. Final sample size calculation taking into account 10% lost-to-follow-up

¹Calculated by inflating the sample size using considering 10% lost-to-follow-up

4. ANALYSIS POPULATIONS

4.1 Study population data sets

Safety population

The safety analysis will be based on the intention-to-treat (ITT) population, defined as all participants who were randomized in the trial.

Efficacy population

The efficacy analysis will be based on the ITT population. For the handling of missing data, the worstcase scenario will be considered, considering all individuals without efficacy data as treatment failures. **Population PK analysis (phase II)** A complete description of the pk analysis can be found in the statistical analysis plan for pharmacokinetics.

For population pharmacokinetic analysis, the 126 participants included in the 3 arms of phase II (26 in arm 1, and 50 in the arms 2 and 3) will be randomly assigned to different subgroups (7 subgroups for arm 1, and 10 subgroups for arm 2 and 3) with different sampling times (2 blood samples per subgroup for arm 1 and 2, and 2 blood samples plus predose on Day 2 per subgroup for arm 3). The two sampling times has been randomly obtained from two different post-dosing ranges covering from 1 to 7 hours (range I) and from 8 to 72 hours (range II). Thus, the overall sampling times describes the entire pharmacokinetic profile for the two drugs (Ivermectin and Albendazole) for each of the 3 groups of body weight (Group 1: 23-30kg, Group 2: 30-45kg, and Group 3:15-23kg).

For the random assignment of the blood capilar extractions (with Mitra (40) Clamshell), a randomization of the times of PK extraction (9 points for arm 1 and 11 and 12 points for arms 2 and 3

respectively) will be carried out carried out for each arm of treatment: [+1h, +2h, +3h, +4h, +5h, +6h, +7h, +8h and +24h] for the arm 1 (albendazole treatment); and [+1h, +2h, +3h, +4h, +5h, +6h, +7h, +8h, +24h, +48h and +72h] for the arm 2 (coadministration IVM+Albendazole); and [baseline preadministration on Day 2 and +1h, +2h, +3h, +4h, +5h, +6h, +7h, +8h, +24h, +48h and +72h] for arm 3 (coadministration IVM+Albendazole)x3 consecutive days)..

For Arm 1 (albendazole treatment), the 9 points (+1h, +2h, +3h, +4h, +5h, +6h, +7h, +8h and +24h) has been divided in 2 groups:

i) One group of 5 points comprising the points from +1h until +5h

ii) One group of 4 points comprising the points from +6h until +24h

For assigning the 2 points we randomize 1 time from each group

For Arm 1 (5 subgroups of 4 participants + 2 subgroups of 3 participants):

SubGroup 1 (n=4): +3h, +6h SubGroup 2 (n=4): +4h, +24h SubGroup 3 (n=4): +2h, +8h SubGroup 4 (n=4): +5h, +7h SubGroup 5 (n=4): +1h, +7h SubGroup 6 (n=3): +2h, +24h SubGroup 7 (n=3): +4h, +8h

For Arm 2 (albendazole + ivermectin treatment), the 11 points (+1h, +2h, +3h, +4h, +5h, +6h, +7h, +8h, +24h, +48h, +72h) has been divided in 2 groups:

i) One group of 6 points comprising the points from +1h until +6h

ii) One group of 5 points comprising the points from +7h until +72h

For assigning the 2 points we randomize 1 time from each group For Arm 2 (10 groups of 5 participants):

SubGroup 1 (n=5): +4h, +72h SubGroup 2 (n=5): +5h, +48h SubGroup 3 (n=5): +2h, +8h SubGroup 4 (n=5): +1h, +8h SubGroup 5 (n=5): +3h, +72h SubGroup 6 (n=5): +4h, +24h SubGroup 7 (n=5): +3h, +7h SubGroup 8 (n=5): +2h, +48h SubGroup 9 (n=5): +5h, +7h

For Arm 3 (10 groups of 5 participants), (albendazole + ivermectin treatment x 3 consecutive days), we follow the same schedules as for Arm 2, but adding predose on Day 2 and starting the extractions from that point, as follows

SubGroup 1 (n=5): predose Day 2, +4h, +72h SubGroup 2 (n=5): predose Day 2, +5h, +48h SubGroup 3 (n=5): predose Day 2, +2h, +8h SubGroup 4 (n=5): predose Day 2, +1h, +8h SubGroup 5 (n=5): predose Day 2, +3h, +72h SubGroup 6 (n=5): predose Day 2, +4h, +24h SubGroup 7 (n=5): predose Day 2, +3h, +7h SubGroup 8 (n=5): predose Day 2, +2h, +48h SubGroup 9 (n=5): predose Day 2, +5h, +7h SubGroup 10 (n=5): predose Day 2, +1h, +24h

Global Health

Sensitivity analysis populations

ISGIODAI Barcelona Institute for

Safety sensitive populations: A per-protocol analysis will be performed including all randomized participants who received at least one dose of medication.

Efficacy sensitive population: A per-protocol analysis will be conducted, including all randomized participants who received at least one dose of medication, did not withdraw, without major protocol deviations, and were not lost to follow-up. Also, participants who did not meet the inclusion or exclusion criteria, received an incorrect treatment, or were administered an incorrect dose will be excluded from the per-protocol analysis.

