# 9.3 ANALYSES POPULATIONS

- Intention-to-Treat (ITT) population: defined as all randomized participants with valid informed consent.
- Modified Intention-to-Treat population: defined as all participants who took at least one dose of study intervention and/or have some particular amount of follow-up outcome data.
- Safety population: defined as the subset of participants for whom safety analyses will be conducted (e.g., participants who took at least one dose of study intervention).

Version 4.0

21st January 2022

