#### 9.5.4 SAFETY ANALYSES

For the safety analysis in phase III, the ITT (those participants who have received at least one dose of study intervention) will be used for the analysis and participants will be considered by arm and by both FDC arms pooled (overall) and by number of doses of FDC received to explore dose-responses. Drug-related AEs will be analysed using ordinal logistic regression with the untoward effect classified as absent, mild,

Version 4.0

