5.5.1 Adverse events

All AEs will be coded using the latest version of MedDRA at the time of the database lock. The actual version of the MedDRA coding dictionary used will be noted in the AE tables and listings.

Treatment-emergent adverse events (TEAEs) are defined as adverse events that occur or worsen on or after the first dose of study treatment.

The severity of the adverse events is assessed by the investigator as mild, moderate, or severe. The relationship to the study drug is determined by the investigator as definite, probably, possibly, unlikely, or unrelated. The categories "unrelated" and "unlikely" will be mapped to "unrelated", the categories "possibly", "probably" and "definite" will be mapped to "related".

An adverse event is considered a serious adverse event (SAE) if it results in any of the following outcomes: 1) results in death, 2) is a life-threatening adverse event, 3) requires hospitalization or prolongation of existing hospitalization, 4) results in a persistent or significant disability/incapacity or substantial disruption of the ability to conduct normal life functions, or 5) a congenital anomaly/birth defect.

An overall summary of TEAEs will be presented showing the number and percentage of participants with: any TEAE, any study drug-related TEAE, any severe TEAE, any treatment-emergent SAE, any study drug-related treatment-emergent SAE, any TEAE leading to study discontinuation, and any TEAE leading to death.

The following TEAEs will be summarized as frequency and percentage of participants by SOC and PT:

- TEAEs
- TEAEs by descending PT
- Severe TEAEs
- Study drug-related TEAEs
- Treatment-emergent SAE
- Study drug-related treatment-emergent SAE
- TEAEs leading to study discontinuation

All adverse events for each patient, including the same event on multiple occasions, will be listed, indicating the preferred term.

Drug-related TEAEs will be analysed using ordinal logistic regression with the untoward effect classified as absent, mild, moderate, or severe and the factorial treatment regimens (without interaction term) as predictor variables. For a count outcome such as the number of TEAEs or treatment-emergent SAEs incidence rate ratio (IRR) and its 95% CI will be computed using Poisson or Negative binomial regression.

The following by-participant listings will be provided:

- AEs
- SAEs
- TEAEs leading to study drug withdrawal
- TEAEs leading to study drug interruption
- TEAEs leading to study discontinuation

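### SAP 4.1 takes all randomised participants as the safety set, in conflict with the protocol's at-least-one-dose set and with the SAP's own TEAE definition; any undosed child lowers that arm's TEAE percentages

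*SAP*

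**What the plan says.** The two documents describe the safety set in several places.

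- **SAP 4.1, safety population:** "The safety analysis will be based on the intention-to-treat (ITT) population, defined as all participants who were randomized in the trial". Dosing is not a condition, and the statement is not limited to one phase.
- **SAP 5.5:** Phase III uses the safety population. No separate set is named for Phase II, where safety is the primary endpoint. SAP 4.1 therefore governs both phases.
- **SAP 4.1, sensitivity populations, for safety:** "A per-protocol analysis will be performed including all randomized participants who received at least one dose of medication".
- **Protocol 9.3, safety population:** those for whom safety analyses will be done, illustrated by "e.g., participants who took at least one dose of study intervention". The same section lists ITT separately, "defined as all randomized participants with valid informed consent".
- **Protocol 9.5.4, Phase III safety:** "the ITT (those participants who have received at least one dose of study intervention) will be used for the analysis".
- **SAP 5.5.1:** "Treatment-emergent adverse events (TEAEs) are defined as adverse events that occur or worsen on or after the first dose of study treatment".
- **SAP 5.1.1:** percentages use the population count in each treatment group as denominator unless otherwise specified.

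Both documents foresee children who are randomised but not treated. SAP 5.2.1 reports them in the disposition summary, and protocol 7.2 allows them to be replaced.

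**The concern.** A safety percentage should describe children who were exposed. Under SAP 4.1 a never-dosed child enters the denominator of every TEAE percentage although the SAP's own definition bars that child from having a TEAE. In the ordinal model of SAP 5.5.1 the child is always in the no-event category, and in the Poisson or negative binomial model always a zero count. Baseline (SAP 5.1.2) and study day (SAP 5.1.3) are defined from the first dose, so neither is properly defined for such a child.

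The labels add to the problem. Protocol 9.5.4 calls the dosed set ITT, against the protocol's own ITT definition, and SAP 4.1 calls it per-protocol. Two programmers could produce different adverse-event tables and each cite a governing text.

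At stake are the TEAE percentages and model-based rates reported for the Phase II primary endpoint and for Phase III safety.

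**Working it through.** The documents state no figure that depends on this definition, so there is none to reproduce. The check compares the definitions and then works through the denominator.

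**Which set each text uses**

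| Text | Dose required? | Label |
|---|---|---|
| SAP 4.1, primary | No | Safety population = ITT |
| SAP 5.5 | Inherited from SAP 4.1 | Safety population |
| SAP 4.1, sensitivity | Yes | Per-protocol |
| Protocol 9.3 | Yes, by example only | Safety population |
| Protocol 9.5.4 (Phase III) | Yes | ITT |

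**Inputs**

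- Phase II arm sizes: ALB 26, FDCx1 50, FDCx3 50 (protocol synopsis; SAP 3.4).
- Undosed children per arm, k: not in the documents. Assumed 0, 1, 2 or 5.
- TEAE proportion among dosed children, p: not in the documents. Assumed 20%; the multiplier does not depend on it.

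**Arm-level percentage**

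Reported proportion = p × (dosed / randomised).

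For an FDC arm with 50 randomised and p = 20%:

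- k = 0: 20% × 50/50 = 20.0%
- k = 1: 20% × 49/50 = 19.6%
- k = 2: 20% × 48/50 = 19.2%
- k = 5: 20% × 45/50 = 18.0%

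If undosed children are replaced, as protocol 7.2 allows, 50 are dosed and 50 + k randomised: 20% × 50/51 = 19.6%, 20% × 50/52 = 19.2%, 20% × 50/55 = 18.2%.

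For the ALB arm of 26, the multiplier is 25/26 = 0.96 with one undosed child and 24/26 = 0.92 with two.

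**Between-arm ratio**

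Reported ratio = true ratio × (dosed fraction in FDC) / (dosed fraction in ALB).

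Assume 20% in ALB and 30% in an FDC arm, a ratio of 1.50:

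- 2 of 50 FDC undosed: 1.50 × 0.96 = 1.44
- 5 of 50 FDC undosed: 1.50 × 0.90 = 1.35
- 2 of 26 ALB undosed: 1.50 / (24/26) = 1.625, about 1.63
- Equal undosed fractions: no change

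**Stopping rules**

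The Phase II rules (SAP 3.6) act on at least one and at least two events, with no denominator. The interim rule is set against participants recruited, 12 in 612 (2% × 612 = 12.24), and not against the safety set. None of these rules uses the SAP 4.1 definition.

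**The case against.** The best defence is that the effect is small and the dosed-only result will be produced anyway. Dosing is directly supervised (protocol 6.4), and protocol 8.1 has the drug given once the randomisation number is issued. Randomising the day before the baseline visit is only an option. One undosed child in 50 moves an assumed 20% to 19.6%, while the 95% Wilson interval for 10/50 runs from about 11% to 33%. SAP 4.1 prespecifies the at-least-one-dose analysis, and SAP 5.2.1 will show how many children were untreated. The protocol standard is also soft: 9.3 offers the dosed set only as an example, and 9.5.4 covers Phase III only.

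All of this stands as a limit on size. It does not justify a primary denominator that includes children who cannot have the event, and the soft, mislabelled protocol text is itself a reason to align the documents.

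A reader might infer more than the documents support:

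- **That SAP 5.5 uses yet another set.** It uses the term defined in SAP 4.1 and inherits that definition.
- **That progression to Phase III is affected.** The Phase II rules are event counts and do not change.
- **That a child given another arm's tablet is counted in the wrong arm.** SAP 4.1 says who is included, not how they are assigned to arms. Analysis as randomised is an inference from the ITT label; what the text shows is a missing rule.
- **That the choice always understates harm.** Arm percentages can only fall, but a ratio can move either way.

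**Conclusion.** The point holds as an inconsistency that makes the primary safety set wrong as written. Whenever a randomised child is undosed, that arm's TEAE percentages are too low by exactly the undosed fraction: 2% relative for 1 of 50, about 4% for 1 of 26. Model-based contrasts move only if undosed fractions differ between arms, and then in either direction.

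This rests on SAP 5.1.1 and 5.5.1 being applied as written. The number undosed and the event rates above are assumptions. The true number undosed may be zero, in which case no result changes. Event counts, type, severity, causality and the Phase II stopping rules are unaffected in any case. The planned dosed-only sensitivity analysis mitigates the problem but does not cure it, because it is secondary and misnamed. The change should be made, with the expectation of a small numerical effect.

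**What to change.** 1. In SAP 4.1, define the safety population as all randomised participants who took at least one dose. Make it the primary safety set in both phases throughout SAP 5.5, and name Phase II explicitly.
2. State the assignment rule: by the regimen actually started. A child in the three-day arm who stops early stays in that arm, and the number of doses received is handled in the dose-response analysis already planned in SAP 5.5. A bare rule of treatment received would not do, because it could move such a child, possibly one who stopped for an adverse event, into the single-dose arm.
3. Keep the all-randomised set for efficacy, disposition and listings.
4. Align the labels: remove the e.g. from the safety population in protocol 9.3, remove the ITT label from protocol 9.5.4, and drop the per-protocol label for safety in SAP 4.1.

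The cost is wording in the SAP and protocol. No new data are needed, and sample size and power do not change.

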8.2 SAFETY AND OTHER ASSESSMENTS

Study procedures are specified in the SOA. The Site PI or delegated study physician will observe each participant for 3h after drug administration. A symptom-directed (targeted) physical examination will be performed at screening and when needed to evaluate possible adverse event(s) (i.e. any new symptoms). No physical exam is needed for routine study visits.

Pharmacokinetic Assessments (Phase II component only at Kenya)

Pharmacokinetic (PK) assessments will be conducted in participants in the three arms of the phase II trial (only Kenya). PK sampling (2 timepoints per participants in arm 1 and 2, 3 timepoints for arm 3) will be performed by finger prick using Mitra(40) Clamshell Devices. The 126 subjects included in the 3 arms of treatment will be randomly assigned to 7 subgroups (for arm 1) and 10 subgroups (for arm 2 and 3) with different sampling times (2 blood samples per subgroup) that will be extracted from all the participants.

Version 4.0

21st January 2022

ALIVE Study

The two sampling times are obtained from two different post-dosing ranges covering from 1 to 7 hours (range I) and from 8 to 72 hours (range II). Thus, the overall sampling times describes the entire pharmacokinetic profile for the two drugs (Ivermectine and Albendazole) for each of the 3 groups of body

PK blood sampling (2 timepoints per participant) will cover the following timepoints:

- Albendazole arm: 1, 2, 3, 4, 5, 6, 7, 8 and 24h after treatment administration.
- Single dose FDC arm: 1, 2, 3, 4, 5, 6, 7, 8, 24, 48 and 72 h after treatment administration
- Three-day FDC arm: 1, 2, 3, 4, 5, 6, 7, 8, 24, 48 and 72 h after treatment administration (time points considered respective to the last dose on day 2). For this arm, 1 additional timepoint will be collected for all participants at pre-dose Day 2.

PK data generated during the phase II component will be analysed according to the Statistical Analysis Plan.

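### The PK sampling plan states two incompatible pairs of time ranges: 32 of 126 children get no post-dose sample at 8–72 h, +6 h is unused in the FDC arms, and no stratification by weight group is stated although coverage of each weight group is claimed

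*SAP*

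**What the plan says.** **General rule.** Protocol 8.2 states: "The two sampling times are obtained from two different post-dosing ranges covering from 1 to 7 hours (range I) and from 8 to 72 hours". SAP 4.1 repeats it: "two different post-dosing ranges covering from 1 to 7 hours (range I) and from 8 to 72 hours (range II". Both go on to say that, taken together, the times describe the whole profile of both drugs in each of the three body-weight groups.

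**Working rule.** SAP 4.1 then divides the times differently by arm and draws one time from each part.
- ALB: "One group of 5 points comprising the points from +1h until +5h" and "One group of 4 points comprising the points from +6h until +24h".
- FDCx1: "One group of 6 points comprising the points from +1h until +6h", with the second part running from +7 h to +72 h.
- FDCx3: the FDCx1 schedules, plus a predose sample on Day 2.

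**Subgroups.** The resulting list has seven ALB subgroups and ten per FDC arm. It includes "SubGroup 7 (n=5): +3h, +7h SubGroup 8 (n=5): +2h, +48h SubGroup 9 (n=5): +5h, +7h".

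**Weight.** SAP 4.1 carries out the randomisation of sampling times for each treatment arm and names no stratification by weight group. Exposure in different weight strata is the third secondary objective of phase II (SAP 2.1.1.2). SAP 2.2.2 plans a population PK model and also a non-compartmental analysis giving Cmax, Tmax and AUC. SAP 4.1 refers to a separate PK analysis plan for the full description.

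**The concern.** The statement that each weight group's profile is covered rests on the 1–7/8–72 h rule, but the subgroups were drawn under another rule. The difference decides which samples are taken. A child with times +5 h and +7 h adds nothing after dosing to the late part of the curve, where elimination is seen.

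With two post-dose samples per child, a non-compartmental curve for a weight group has to be built by pooling children at each nominal time. A time at which a weight group has no child is then a gap in that group's curve. If assignment does not take account of weight, nothing in the plan prevents such gaps. The listed time +6 h is also never sampled in either FDC arm.

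**Working it through.** **1. Reproduce the stated total.** ALB: 5 × 4 + 2 × 3 = 26. FDCx3: 10 × 5 = 50. FDCx1: nine subgroups are legible in the text available (45 children). SAP 4.1 says FDCx3 follows the FDCx1 schedules, so FDCx1 subgroup 10 is taken from the FDCx3 list (+1 h, +24 h), giving 50. Total 26 + 50 + 50 = 126, as stated. The missing line may be a loss in text extraction and is not counted as an error.

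**2. Test each pair against the two rules.** Every pair obeys the arm-specific split. Against 1–7/8–72 h, these fail:

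| Arm | Subgroups with both post-dose times ≤7 h | Children |
|---|---|---|
| ALB | 1 (+3, +6), 4 (+5, +7), 5 (+1, +7) | 4 + 4 + 4 = 12 of 26 |
| FDCx1 | 7 (+3, +7), 9 (+5, +7) | 5 + 5 = 10 of 50 |
| FDCx3 | 7, 9 (same times) | 5 + 5 = 10 of 50 |
| All | | 32 of 126 (25.4%) |

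The 10 FDCx3 children also give a predose Day 2 sample. Children with only samples at or before 7 h are therefore 12 + 10 = 22 of 126 (17.5%). Neither count depends on the inferred subgroup 10.

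**3. Children per time.**
- ALB: 1 h 4, 2 h 7, 3 h 4, 4 h 7, 5 h 4, 6 h 4, 7 h 8, 8 h 7, 24 h 7.
- Each FDC arm: 10 at each of 1, 2, 3, 4, 5, 7, 8, 24, 48 and 72 h; 0 at 6 h.

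**4. Weight-by-time cells if assignment ignores weight.** The documents do not give arm-by-weight numbers. Applying the phase II allocation probabilities to groups of 38, 38 and 50 gives 0.4 × (38, 38, 50) = 15.2, 15.2, 20 per FDC arm and 0.2 × (38, 38, 50) = 7.6, 7.6, 10 in ALB. Assumed sizes are 15/15/20 and 8/8/10.

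For one FDC time with 10 children, the chance that a given weight group is absent is:
- group of 15: C(35,10)/C(50,10) = 1.8%
- group of 20: C(30,10)/C(50,10) = 0.3%

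The expected number of empty cells per FDC arm is 10 × (2 × 0.0179 + 0.0029) ≈ 0.39 of 30. Cells share children, so the chance of at least one empty cell was simulated (40,000 random assignments): about **31% per FDC arm** and **91% in ALB**. For times of 24 h or later it is about 11% per FDC arm.

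**5. Effect of redrawing the pairs alone.** Change FDC subgroup 7 to (+6, +24) and subgroup 9 to (+7, +48). In ALB, use early times 1 to 7 h once each, paired with +8 h or +24 h. Then 0 of 126 children lack a post-dose sample at 8–72 h and all 11 FDC times are used. Several times now have only 3 to 5 children, however. Without stratification by weight, the chance of at least one empty cell rises to about 85% per FDC arm and over 99% in ALB.

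**The case against.** The strongest reply is that the table does follow a rule. The arm-specific splits are printed beside the subgroup list and every pair obeys them. The general range cannot apply literally to ALB, whose sampling stops at 24 h. A reader might infer that the table ignores its own rule; the documents do not support that. They contain two rules that need reconciling, and correcting the summary sentence would be one way to do it. This part of the reply stands.

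Three further stronger readings also fail:
- **A quarter of the children give no late information.** FDCx3 children give a predose sample on Day 2, about a day after their second dose, so the count falls to 22. Of these, 12 are ALB children, who carry no ivermectin information. Among FDC children it is 10 of 100.
- **Subgroups are assigned without regard to weight.** The SAP is silent on this. The separate PK plan was not available, and it may say more.
- **The weight-group profile cannot be described.** About 0.39 empty cells of 30 are expected per FDC arm. A population model borrows across children and times and tolerates some gaps. The +5 h and +7 h samples (10 children each per FDC arm) bracket the missing +6 h. No loss of precision in AUC or Cmax has been shown.

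The reply does not remove the contradiction itself or the unused listed time. It also leaves a coverage statement that assignment by arm alone does not secure. The population model is not the only planned analysis, and pooled non-compartmental summaries by weight group do not tolerate empty cells in the same way.

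**Conclusion.** The point holds in a limited form. Two incompatible range definitions stand in the plan. The coverage claim rests on one and the sampling list follows the other. By exact count, 32 of 126 children have no post-dose sample at 8–72 h, 22 of 126 have only samples at or before 7 h, and 0 of 100 FDC children are sampled at +6 h. The +6 h count for FDCx1 uses the subgroup inferred from the FDCx3 list.

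Coverage by weight group is asserted but not secured by anything stated. The 31% and 91% figures assume 15/15/20 and 8/8/10 children and assignment that ignores weight. They give the chance of any gap, not of many. The consequence is for a phase II secondary objective; the phase II primary objective is safety and is not affected.

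**What to change.** 1. **Assign PK subgroups within weight group**, from a list prepared per arm and weight group, so that each weight group appears in every subgroup. At the assumed sizes this is feasible: at least 15 children over 10 FDC subgroups, and 8/8/10 over the seven ALB subgroups of 4, 4, 4, 4, 4, 3 and 3. Sequential enrolment by weight group makes such lists practical. Simple randomisation to arms may leave fewer than seven ALB children in a weight group; the list should then cover as many subgroups as it can.

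2. **Together with step 1, not alone, reconcile the ranges** in Protocol 8.2 and SAP 4.1. The preferred route is to redraw the pairs to 1–7/8–72 h, for example as in step 5 of the working. The alternative is to keep the pairs, correct the stated ranges, explain the absence of +6 h and narrow the coverage statement.

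**Cost.** A revised subgroup table and new lists, with the same children and the same number of finger pricks. Under the redraw, +3 h, +5 h and +7 h each fall from 10 to 5 samples per FDC arm, while +24 h and +48 h rise from 10 to 15. In ALB, +2 h and +4 h fall from 7 to 3–4 and +7 h from 8 to 3–4.

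**If sampling is already complete**, correct the stated ranges, tabulate the samples by weight group and time, and limit the coverage claim to what was observed.
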